#### 4.1.1.Stop go criteria

Details of the 'Stop'/'Change'/'Go' criteria derived from data collected in this feasibility study will determine progression to a future large-scale evaluation (c-RCT).

Below is a table of the revised progression Criteria for the CONNECT feasibility study. The criteria were agreed with the study advisory group (SAG) prior to starting recruitment. These criteria will be used to determine whether a full c-RCT would be feasible.

Progression Criteria	Green- Go	Amber- Maybe	Red- Stop	Proposed action if Amber targets are attained
Cluster recruitment targets : Number of Cardiac Centres recruited in the first 3 months of the study.	8	5-7	≤4	Review reasons for non-participation on EoI document and consider alternative strategies.

Progression Criteria	Green- Go	Amber- Maybe	Red- Stop	Proposed action if Amber targets are attained
Patient recruitment targets : Average number of patients recruited per month, per cluster.	3+	2	≤1	Review recruitment processes and reasons for non-consent. Consider alternative strategies.
Adherence targets: % of the patient sample who access CONNECT before pre-assessment clinic. *	60%+	25%- 60%	<25%	Review qualitative data for reasons for non-adherence. Consider strategies to improve CONNECT engagement. Consider developing a non-digital version of CONNECT if non-adherence is largely due to low digital literacy levels.
Retention targets : % of the patient sample who complete the study.	80%+	60%- 80%	<60%	Review attrition reasons and identify strategies to prevent before full c-RCT.
Willingness to be randomised: % of Cardiac Centres who responded to the EOI that are willing to be randomised in the future c-RCT.	80%	60%- 80%	<60%	Review reasons for non-participation on EoI document and consider alternative strategies and/or trial designs, such as delayed-intervention trial.
Anticipated Primary Outcome acceptability: Average % item completion of the Time Point 2 Decisional Conflict Scale questionnaire. †	80%+	60%- 80%	<60%	Review the outcome measures with PPI group and revise ahead of c-RCT.
Patient and Cardiology Health Professional acceptability of CONNECT and study procedures.	-	-	-	Review qualitative data on patient and cardiology health professional acceptability of CONNECT.
Adverse events: Adverse events linked to using CONNECT.	-	-	-	There are no known serious adverse events linked to using a patient decision aid such as CONNECT. We will review any patient-reported negative effects of using CONNECT during the pre- assessment clinic. Treatment may continue without the use of CONNECT.

\*Based on data from a study that found 62% patient uptake of a smartphone app to self-test vision (Korot E, Pontikos N, Drawnel FM, Jaber A, Fu DJ, Zhang G, Miranda MA, Liefers B, Glinton S, Wagner SK, Struyven R, Kilduff C, Moshfeghi DM, Keane PA, Sim DA, Thomas PBM, Balaskas K. Enablers and Barriers to Deployment of Smartphone-Based Home Vision Monitoring in Clinical Practice Settings. JAMA Ophthalmol. 2022 Feb 1;140(2):153-160. doi: 10.1001/jamaophthalmol.2021.5269).

*†Based on data from a Randomised Controlled Trial of a patient decision aid for angina, in which the lowest item response rate for the post-visit decisional conflict scale (DCS) was 83% (21 responses missing for the Effective subscale of the DCS; total sample n=124). Coylewright M, Dick S, Zmolek B, et al. Percutaneous Coronary Intervention Choice Decision Aid for Stable Coronary Artery Disease: A Randomized Trial. Circulation Cardiovascular quality and outcomes 2016 2016/11/03. DOI: 10.1161/circoutcomes.116.002641.* 

This information along with the acceptability of the study design and protocol to patients; patient recruitment and attrition/retention rates will enable us to determine whether or not the definitive c-RCT is feasible.

There are no planned sensitivity or subgroup analyses.

#### 4.2. Missing data

As this a feasibility study, no methods to deal with missing data will be used.

We will report the number of patients who had complete data for each of the key parameters (each outcome measure) for each time-point by treatment group and overall.

For patient questionnaires, the item response rate at each visit (Enrolment, T1, T2) will be reported. Response rate will be measured as a fraction of the total number of items.

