8.2.2 Patient recruitment and enrolment

A Clinical Research Nurse, or delegate, will liaise with the local PI, or delegate, and send study information pack to interested patients. The Clinical Research Nurse, or delegate, will then telephone eligible patients 3-5 days later. Completion of the Screening Log and the Enrolment and Withdrawal Log will determine the following outcomes:

- Number of patients approached by the Clinical Research Nurse.
- Number of patients who were unable to be contacted.
- Number of patients who declined participation, with reasons, where given.
- Number of participants without digital access (internet or device).

Following informed consent and enrolment into the study, the research nurse will administer the 3-item BRIEF Health Literacy Screening Tool²¹ and the 8-item eHEALS: eHealth Literacy Scale²² to participants during the telephone call and record responses in the electronic questionnaire document and enter the data into the site's Case Report Form. The Clinical Research Nurse, or delegate, will also remind participants to complete and return the baseline (T1) questionnaires, which will have already been sent to participants with the study information pack. They will also document the outcomes below in a Case Report Form:

- Patient participant demographics such as but not limited to age, gender, ethnicity, level of social support (live alone), employment.
- Relevant medical history; cardiac diagnosis, co-morbidities.

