8.2.3 Baseline

Participants will have received the baseline (T1) questionnaires in the study information pack. This will include instructions to complete them within 7 days of consenting to participate and return in the stamped-addressed envelope or via e-mail to the Research Fellow. The baseline (T1) questionnaires are the 10-item Decisional Conflict Scale²³ and the bespoke coronary angioplasty knowledge questionnaire. The Research Fellow will collate returned questionnaires to determine the following outcomes:

- Number of returned self-report questionnaires at baseline (T1).
- Item response rate (Number of valid responses on each questionnaire divided by total number of responses requested).
- Number of patients who had complete data for each questionnaire at baseline.

Participant answers and questionnaire scores will be input into a CRF by the Research Fellow.

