8.2.5 Post pre-assessment clinic (T2) questionnaires

The Clinical Research Nurse, or delegate, will liaise with the pre-assessment lead nurse weekly to update them about which patient participants had consented to study participation and attended the pre-assessment consultation. Participants at all eight clusters who attended the pre-assessment consultation will be sent four T2/Follow-up questionnaires: the Decisional Conflict Scale²³, the Coronary Angioplasty Knowledge questionnaires sent at T1/Baseline and the 10-item Preparation for Decision-Making Scale²⁴ and 13-item Perceived Involvement in Care Scale²⁵. The latter two questionnaires are validated tools designed to evaluate the quality of the decision-making process²⁶. Two extra questions will be included at the end of the Angioplasty Knowledge questionnaire to evaluate what health information patients accessed ahead of planned coronary angioplasty and their satisfaction with discussions about treatment options. In the intervention arm, two extra questions will ask whether participants were able to access CONNECT and take the personal summary to the pre-assessment appointment. Participants will be instructed to complete and return them to the Research Fellow within 7 days of receipt using the stamped-addressed envelope.

The Research Fellow will collate returned questionnaires to determine the following outcomes:

- Number of returned self-report questionnaires at post-pre-assessment.
- Number of patients who had complete data for each questionnaire at post-preassessment.
- Item response rate (Number of valid responses divided by total number of responses requested).
- Retention: defined as the proportion of participants completing the anticipated primary outcome questionnaires (i.e., completing the Decisional Conflict Scale questionnaire at T2/after pre-assessment).
- CONNECT adherence: The percentage of patient participants in the intervention arm who report being able to successfully access CONNECT and take the personal summary to the pre-assessment consultation

Participant answers and questionnaire scores will be input into a CRF by the Research Fellow.

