Intra-cluster Correlation Coefficient (ICC) and sample size calculation for full scale c-RCT	
 
Estimate of the ICC of the Decisional Conflict Scale at T2 using a marginal or random effects model.
 
The full c-RCT sample size will be calculated based on estimates of the effect size (alongside previous research), the standard deviation and the ICC from the anticipated primary outcome analysis.
 

Practicality of implementing CONNECT in NHS settings	
 
CONNECT implementation:         
 
Number of participants who access CONNECT.
 
Percentage of pre-assessment clinic visits in which the CONNECT summary was used during the consultation.
 
Qualitative analysis of training session minutes and interview transcripts to summarise:                 
 
Potential variations in usual-care patient pathway for planned coronary angioplasty.
 
Practicalities of providing a digital PtDA in the NHS.
 
Barriers and enablers to integrating the CONNECT summary.
 
 
 

Reasons for non- consent to study participation	Qualitative analysis to summarise: • Reasons for Cardiology Departments nonparticipation. • Reasons for patient nonparticipation.

Uncertainty	Outcomes
Acceptability of	Qualitative analysis of interviews to explore:
CONNECT and study procedures	
 
Self-reported adherence to CONNECT and how it was used by patients at home and during the pre-assessment clinic.
 

	
 
Barriers and enablers to recruitment and using CONNECT at home and during pre-assessment clinic.
 

	
 
Understanding, appropriateness, and potential burden of questionnaire completion.
 

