#### 3.3. Analysis populations

The Intention To Treat (ITT) population includes all patients for whom consent is obtained and who are randomised to treatment. This is the primary analysis set and endpoints will be summarised for the ITT population unless stated otherwise.

The Per Protocol (PP) population includes all patients who accessed CONNECT on the treatment arm. This is a secondary analysis set.

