## 4. Analysis

#### 4.1. Analysis methods

As this is a feasibility study the main analysis will be predominantly descriptive and focus on confidence interval estimations rather than formal hypothesis testing. The baseline demographics and clinical characteristics of the patients will be reported overall and by randomised group. For the continuous variables (e.g., age) either mean and SD will be presented or median and inter quartile range (IQR) depending on the distribution of the data. The number of observations used in each calculation will be presented alongside the summaries.

We will look at differences between groups for the anticipated primary outcome (Decisional Conflict Scale). A random effects model (or another appropriate method) will be used to estimate the difference between the two treatment groups adjusting for age, sex, health literacy score, living alone, health burden (number of co-morbidities) and baseline decisional conflict scale score as fixed effects and hospital as a random effect to account for clustering. This difference and its associated 95% confidence interval will be used to check that the likely effect is within a clinically relevant range (as confirmation that it is worth progressing with the full trial) and to inform the sample size calculation for the definitive study as outlined previously. Similar analyses will be conducted for other secondary endpoints.

For the anticipated primary outcome (Decisional Conflict Scale) at follow up, the ICC for patients treated with the same site will be estimated using a marginal or random effects model.

The mean/median for anticipated primary and secondary outcomes (e.g. Coronary Angioplasty Knowledge questionnaire) at baseline and post-pre-assessment (along with its variability) will be reported for all participants.

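### Participants with a follow-up Decisional Conflict Scale score but no returned baseline form drop out of the adjusted effect estimate, a modest and avoidable loss of precision

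*SAP*

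**What the plan says.** - **Effect model (SAP 4.1).** The DCS difference comes from a random effects model "adjusting for age, sex, health literacy score, living alone, health burden (number of co-morbidities) and baseline decisional conflict scale score as fixed effects", with hospital as a random effect. The SAP allows some other suitable method but names none.
- **Missing data (SAP 4.2).** The SAP states that "no methods to deal with missing data will be used". SAP 4.1.1 plans no sensitivity analyses and SAP 4.3 no additional ones. Completeness is reported per measure, time-point and group.
- **T1 return (Protocol 8.2.3).** The baseline forms arrive in the study pack. Participants are told to "complete them within 7 days of consenting to participate and return in the stamped-addressed envelope or via e-mail to the Research Fellow".
- **Other covariates (Protocol 8.2.2).** At the enrolment call "the research nurse will administer the 3-item BRIEF Health Literacy Screening Tool", and demographics and history go on the case report form. T1 DCS is therefore the covariate most exposed to non-return.
- **T2 dispatch (Protocol 8.2.5).** "Participants at all eight clusters who attended the pre-assessment consultation will be sent four T2/Follow-up questionnaires". Return of T1 is not a condition. Retention, here and in SAP Table 1, is completion of the DCS at T2.
- **Analysis set (SAP 3.3).** "The Intention To Treat (ITT) population includes all patients for whom consent is obtained" and who are randomised; this is the primary set.
- **ICC and SD.** SAP 4.1 says that for follow-up DCS "the ICC for patients treated with the same site will be estimated using a marginal or random effects model" and names no covariates. SAP Table 1 bases the full-trial size on the effect size, "the standard deviation and the ICC from the anticipated primary outcome analysis".

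**The concern.** The SAP never uses the term complete-case, but that is what results. A regression that includes T1 DCS and has no rule for missing values drops every participant whose T1 score is absent. T1 and T2 are returned separately, so some participants will have T2 without T1. They count towards retention and have the anticipated primary outcome, yet contribute nothing to the estimated difference.

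That estimate has a use. SAP 4.1 takes the difference and its 95% confidence interval as a check that the likely effect is clinically relevant, and as an input to the size of the definitive trial. SAP 2.4 adopts a precision framework, so discarding observed outcomes works against the plan's own aim. The loss would also be hard to see, because counts per measure and time-point do not show how many participants have both T1 and T2.

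**Working it through.** **1. The plan's own figures.** SAP 2.3.2 gives 24 to 42 clusters and 914 to 1618 patients (effect 0.4 to 0.3 SD, ICC 0.05, mean cluster size 40, 90% power, two-sided 5%). The t-test needs 132.31 or 234.46 per arm. The variation in cluster size is not stated; an assumed coefficient of variation of 0.5 gives a design effect of 1 + ((1 + 0.25) × 40 − 1) × 0.05 = 3.45.
- 132.31 × 3.45 = 456.5, so 457 per arm, 914 in total, 12 clusters per arm.
- 234.46 × 3.45 = 808.9, so 809 per arm, 1618 in total, 21 clusters per arm.

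Both match, so the ICC of 0.05 is used as the plan uses it.

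**2. Inputs for the check.** Eight clusters of 40, six against two (SAP 1.1, 2.3.1). ICC 0.05 (SAP 2.3.2). T2 retention 80%, the green threshold in SAP 4.1.1. The share p of T2 responders who also have T1 is my assumption, because the documents give no figure.

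**3. Effect estimate.** In SD units, with m analysed per cluster,

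SE = √[(0.05 + 0.95/m) × (1/6 + 1/2)], where m = 40 × 0.80 × p.

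| p | m | N | SE (SD) | Rise |
|---|---|---|---|---|
| 100% (all T2 responders) | 32.0 | 256 | 0.230 | – |
| 95% | 30.4 | 243 | 0.233 | 1% |
| 90% | 28.8 | 230 | 0.235 | 2% |
| 80% | 25.6 | 205 | 0.241 | 5% |
| 60% | 19.2 | 154 | 0.258 | 12% |

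Worked row, p = 80%: 0.95/25.6 = 0.0371; (0.05 + 0.0371) × 0.6667 = 0.0581; square root 0.241.

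**4. Why the rise is small.** With unlimited patients per cluster the SE would still be √(0.05 × 0.6667) = 0.183. The number of clusters, two of them control, sets most of the uncertainty. The 95% half-width (1.96 × SE) moves from 0.45 to 0.47 SD at p = 80%; with a t distribution on 6 degrees of freedom it moves from 0.56 to 0.59. All of these exceed the 0.3 to 0.4 SD effect in SAP 2.3.2.

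**5. Effect of baseline adjustment.** Adjustment shrinks the within-cluster variance by 1 − r², where r is the T1–T2 correlation (assumed). At p = 80%, the adjusted complete-case SE is 0.99 times that of an unadjusted model on all T2 responders if r = 0.5, and 1.03 times if r = 0.3.

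**6. SD and ICC, only if taken from the adjusted model.** With Swiger's formula, eight clusters and ICC 0.05, SE(ICC) would go from 0.041 to 0.042, 0.045 or 0.052 at p = 95%, 80% or 60%. The relative SE of the SD, 1/√(2(N − 1)) ignoring clustering, would go from 4.4% to 4.5%, 5.0% or 5.7%. If both are estimated from T2 scores without T1, neither loss occurs.

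**The case against.** The strongest reply is that little is lost. The T1 form comes in the study pack, the nurse reminds participants on the consent call, and it may be e-mailed back. Those who return T2 are likely also to have returned T1, so p may be nearer 95% than 80%. The study is descriptive and not powered for effect, no progression criterion in SAP 4.1.1 uses the effect, SD or ICC, and the effect informs sizing only alongside earlier research. All of this stands, and it limits the severity. It does not explain why observed outcomes should be discarded when a routine model keeps them.

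Three stronger readings are tempting, and the documents do not support them.

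- **That the SD and ICC necessarily lose precision too.** The ICC sentence in SAP 4.1 names no covariates, and the same section already plans to report the variability of the outcome at follow-up for all participants. Table 1 does not say whether its source analysis is adjusted. The gap is one of specification.
- **That the analysed cluster size would fall below a required 30 to 50.** SAP 2.3.1 and Protocol 12.1.1 give that range as the point where gains in ICC precision tail off. It is not a minimum for analysis.
- **That keeping all T2 responders restores the intention-to-treat set.** It does not: T2 non-responders remain outside the comparison.

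The remedy also carries an assumption. T1 is completed by unblinded participants after clusters are randomised (Protocol 6.3), with consent forms that differ by arm (Protocol 5.1), so T1 non-return may depend on arm.

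**Conclusion.** The point holds for the adjusted effect estimate and its 95% confidence interval. Read together, SAP 4.1 and 4.2 exclude T2 responders without T1, although the protocol collects their outcome and counts them as retained. At 80% T2 retention and ICC 0.05, the SE rises by about 1%, 5% or 12% when 95%, 80% or 60% of T2 responders have T1. These shares are assumptions; a real figure will come only from the study. Only the loss of precision is quantified here; bias from selecting double responders is possible but not shown. For the SD and ICC the finding is that the source model must be named. Severity is minor to moderate: no progression decision turns on it, and the remedy is cheap.

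**What to change.** In SAP 4.1 and 4.2:

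1. Define the effect analysis set as every participant with a T2 DCS score.
2. Preferably fit T1 and T2 DCS together in one mixed model with hospital and patient random effects, keeping the other covariates. State whether the baseline mean is held common to the arms; with enrolment after cluster randomisation, that is an assumption to declare.
3. A simpler alternative is to fill missing baseline DCS with the overall mean and add a missing indicator, with the caveat that T1 is completed unblinded after cluster randomisation.
4. Show the complete-case result beside the main one.
5. State that the SD and ICC of T2 DCS are estimated on all T2 responders.
6. Report the number with both T1 and T2 by arm.

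The cost is SAP wording, a few lines of R, slightly more modelling and a missing-at-random assumption. No new data are needed.

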#### 4.3. Additional analyses

There will be no additional analyses.

#### 4.4. Harms

It will be the responsibility of the local PI to report any adverse events and escalate to the Chief Investigator as required. The occurrence of an adverse event caused by being in the intervention or control seems very unlikely.

We will record MACE, (acute myocardial infarction, death due to a cardiac or unknown cause, emergency revascularization, ventricular arrhythmia, or cardiogenic shock) that participants may suffer as a complication of treatment with "angio query proceed" or planned coronary angioplasty and hospital readmission within 30 days of treatment. However, this will not be recorded as an adverse event.

Any adverse events will be reported with their number/rate and associated 95% CI. There are no known serious adverse events linked to using a patient decision aid such as CONNECT. Patient-reported negative effects of using CONNECT will be reported during the participant's pre-assessment clinic appointment. Treatment may continue without the use of CONNECT.

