3.3 Stop/Go criteria for progression to future c-RCT

To progress to a full-scale c-RCT, we will need to demonstrate that it is feasible and acceptable to implement CONNECT in the planned coronary angioplasty patient pathway. We will also need to determine the acceptability of study procedures. Progression criteria will guide decisions about advancement to a future large-scale trial. Feasibility data may also inform the study design of other trials that test PtDAs. Table 1 below shows the preliminary Stop/Go criteria that will be developed by the Study Advisory Group and determine progression to the development of an application for a future c-RCT.

Table 1. Stop/go criteria

STOP/GO Criteria	Green- Go	Amber- Change	Red- Stop	Proposed action if Amber targets are attained
Cluster recruitment targets: Number of Cardiac Departments recruited in the first 4 months of the study	8	6-7	≤5	Review reasons for non- participation on Eol document and consider alternative strategies.
Patient recruitment targets: Average number of patients recruited per month, per cluster	4+	3	1-2 (<50% target)	Review recruitment processes and reasons for non-consent. Consider alternative strategies.
Adherence targets: % of the patient sample who access CONNECT before preassessment clinic	75%+	66%- 75%	<66%	Review qualitative data for reasons for non-adherence. Consider strategies to improve CONNECT engagement.
Retention targets: % of the patient sample who complete the study.	80%+	60%- 80%	<60%	Review attrition reasons and identify strategies to prevent before full c-RCT.
Willingness to be randomised: Number of Cardiac Departments (n=98) who are willing to be randomised (anticipated cluster number for full trial: 24 - 42)	33+	24 - 33	<24	Review reasons for non- participation on Eol document and consider alternative strategies and/or trial designs, such as delayed-intervention trial.

Anticipated Primary Outcome acceptability: % patient sample completion of Decisional Conflict Scale questionnaire.	80%+	60%- 80%	<60%	Review the outcome measures with PPI group and revise ahead of c-RCT.
Patient and Cardiology Health Professional acceptability of CONNECT and study procedures.	-	-		Review qualitative data on patient and cardiology health professional acceptability of CONNECT.
Adverse events*: Number of adverse events at one-month follow-up after the preassessment clinic.	0	0	1+	All adverse events will be reviewed by the local PI. Treatment may continue without the use of CONNECT.

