^{*}Potential adverse events linked to using a patient decision aid (CONNECT). Eol: Expression of Interest

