8.2.4 Pre-assessment clinic

Participants at all eight clusters will attend their usual-care pre-assessment clinic consultation with a cardiac nurse specialist which may be in-person or conducted remotely (telephone or online video call). Patient participants in the intervention arm will have received a 'communication' from the hospital confirming their pre-assessment consultation date. This may be a paper or digital letter, email, or text. Instructions on how to access CONNECT, via a web link, or QR code, will be included in the 'communication' and tailored to match the style of the Cardiology Department approach. Participants will be invited to use CONNECT and save their personal summary before attending their usual-care pre-assessment clinic consultation.

Those in the intervention group will be asked if they were able to access CONNECT and the personal summary. If available, the personal summary will be referred to during the consultation. Approaches to integrating the CONNECT summary into consultation will be discussed during the study set up training sessions. If the patient participant fails to attend the clinic consultation, their consultation will be rearranged as per usual care. Immediately following each consultation with a participant, the cardiac nurse specialist will complete the Pre-Assessment Log for collection of the following outcomes:

- Number of missed pre-assessment clinic consultations.
- Number of participants who used the CONNECT summary during the consultation
- Duration of pre-assessment clinic consultation

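### Patient-reported negative effects of CONNECT have one scheduled collection point, the pre-assessment appointment, so the adverse-event rate promised in SAP 4.4 has no defined number of patients asked

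*SAP*

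**What the plan says.** SAP 4.4 (Harms) states that "Patient-reported negative effects of using CONNECT will be reported during the participant's pre-assessment clinic appointment". The adverse-event row of the progression table in SAP 4.1.1 says the same in other words: "We will review any patient-reported negative effects of using CONNECT", again at the pre-assessment clinic, with dashes for Green, Amber and Red. SAP 4.4 also commits to giving any adverse events as a number or rate with a 95% confidence interval. It records MACE and readmission but does not class them as adverse events. SAP 3.3 makes the ITT population the default for summaries.

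Protocol 3.3, Table 1, has a different row: "Number of adverse events at one-month follow-up after the preassessment clinic", with 0 for Green, 0 for Amber and 1 or more for Red. A footnote limits it to "Potential adverse events linked to using a patient decision aid (CONNECT"). The protocol describes its table as "preliminary Stop/Go criteria that will be developed by the Study Advisory Group". Of the revised table, the SAP says: "The criteria were agreed with the study advisory group (SAG) prior to starting recruitment".

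On recording, Protocol 8.2.4 says: "Immediately following each consultation with a participant, the cardiac nurse specialist will complete the Pre-Assessment Log". The outcomes it then lists are missed consultations, use of the CONNECT summary and consultation duration.

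**The concern.** The point is about effects of the tool itself, such as worry, distress or confusion, and not about MACE. A rate with a confidence interval is interpretable only if one knows how many patients were asked and when. The plan names one occasion and does not say that a question is put to the patient there. Protocol 8.2.4 says intervention patients will be asked about access to CONNECT and the summary; it mentions no question about negative effects.

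A low or zero rate could therefore mean few effects or little asking, and the confidence interval would not tell these apart, because it covers sampling error and not missed events. The result still sits in the progression table for review, and a feasibility study should also learn whether harms can be collected in the later trial. Protocol section 9 itself cites national policy that gives asking participants about their experience of the intervention as an example of attending to safety.

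**Working it through.** **1. Routes by which a negative effect could reach the data**

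| Route | Who | When | Described as asking about negative effects? |
|---|---|---|---|
| Pre-assessment appointment (SAP 4.1.1, 4.4) | Intervention attenders | At the visit | Named as the reporting point; no item in the listed log outcomes (Protocol 8.2.4) or the SAP 2.7.4 data list |
| T2 questionnaires (Protocol 8.2.5) | Attenders, both arms | Sent after the visit, return asked within 7 days of receipt | No. Four questionnaires, with extra items on information accessed, satisfaction with discussions and, in the intervention arm, CONNECT access and the summary |
| Interviews (Protocol 4.3, 8.2.6) | Up to 40 of 240 | Within 1-2 weeks of the visit | Experience of CONNECT is explored; topic guide not in the text reviewed |
| Local PI reporting (Protocol 9, SAP 4.4) | Any patient | Any time | Passive; no schedule of asking |
| Record review (Protocol 8.2.7) | All | End of study | No. Treatment received, mortality, MACE and readmission |

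Protocol Table 3 has no row for a patient contact about CONNECT one month after pre-assessment.

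**2. Denominator.** Intervention arm: 6 clusters x 40 = 240, which agrees with Protocol 4.3. SAP 4.4 gives no denominator for the adverse-event rate. If the SAP 3.3 default applies, each intervention patient who was not asked enters as a patient without an event.

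**3. What zero events would show if everyone were asked.** Exact two-sided 95% upper limit = 1 - 0.025^(1/n).

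- n = 240: 1.53%.
- n = 192 (80% of 240): 1.90%.
- n = 144 (60% of 240): 2.53%.

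The 80% and 60% are the retention boundaries in both progression tables, used here as stand-ins for the share answering a T2 item. With events present, dividing by 240 instead of by those asked shrinks the rate by the factor asked/240: 192/240 = 0.80 or 144/240 = 0.60.

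These limits ignore clustering. SAP 2.3.2 assumes an ICC of 0.05, for the Decisional Conflict Scale and not for harms. Borrowed for illustration, it gives a design effect of 1 + (40 - 1) x 0.05 = 2.95, an effective n of 240/2.95 = 81.4, and an upper limit of about 4.4%.

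**4. What zero would show if capture is incomplete.** Let s be the probability that a true event is recorded. The documents give no value, so a range is shown, with n = 240 and no clustering. The chance of recording zero when the true rate is 2% is (1 - 0.02 x s)^240. The limit on the true rate after a recorded zero is about 1.53%/s.

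| s (assumed) | Chance of recording zero | Upper limit on true rate |
|---|---|---|
| 1 | 0.8% | 1.5% |
| 0.5 | 9% | 3.1% |
| 0.25 | 30% | 6.1% |
| 0.1 | 62% | 15.3% |

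**5. The two progression rows.** The protocol has a count, a one-month window and thresholds 0 / 0 / 1+. The SAP has no count threshold and no window, and a review tied to the pre-assessment clinic. They describe different measurements.

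**The case against.** The strongest reply is that light harms collection suits an educational tool. The protocol cites cardiologists' advice and a review of 105 studies that reported no adverse effects (sections 3.8, 9 and 14). CONNECT is meant to be used at home before the visit, so the appointment already follows the main exposure. The Decisional Conflict Scale, given at T1 and T2 in both arms, measures uncertainty and self-reported understanding, so confusion is partly measured after the visit with a control comparison. PI reporting has no cut-off at the visit, and the interviews may bring out negative experiences. Withdrawals are recorded with reasons.

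Much of this stands, and it rules out several stronger readings that a reader might infer:

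- That a zero count drives progression. The one-month rule belongs to the protocol's preliminary table; the SAP's revised table sets no threshold.
- That effects arising when the summary is discussed are missed. That discussion takes place at the appointment the SAP names.
- That patients who miss the visit are never asked. Protocol 8.2.4 says missed consultations are rearranged, so this could apply only to those who never attend.
- That nothing is recorded. The list in Protocol 8.2.4 is not a full account of the log: it also omits CONNECT access, which SAP 3.2 takes from that log. The form itself was not available, so a missing field cannot be concluded.

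What the reply does not remove is that no described question about worry or distress from CONNECT goes to all intervention patients after the visit, and that the promised rate has no stated number asked.

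**Conclusion.** The point holds as a gap in harms ascertainment and reporting; no stated figure in the plan is wrong. The denominator effect alone is modest: the zero-event upper limit moves from 1.5% to 2.5% if 60% rather than all of the arm answer. Incomplete capture matters more. At a true rate of 2%, the chance of recording zero rises from 0.8% to between 9% and 62% over the assumed capture range of 0.5 to 0.1. Those capture values are assumptions, and the calculation treats patients as independent. Whether the SAP 3.3 default governs the adverse-event rate is also an inference, because SAP 4.4 does not say. The mismatch between the two progression rows rests on the text alone and needs no assumption.

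**What to change.** 1. Add one item to the intervention-arm T2 questionnaire, beside the two existing CONNECT questions, asking whether using CONNECT caused worry, distress or other problems.
2. Confirm that the Pre-Assessment Log has a matching field, or add one, and name it in Protocol 8.2.4 and SAP 2.7.4.
3. In SAP 4.4, report the rate separately from MACE, with the number of intervention patients actually asked (those answering the item) as denominator, and show that number beside 240.
4. Reconcile the adverse-event rows of Protocol Table 1 and SAP 4.1.1, including the window. No threshold is proposed here.

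The cost is one questionnaire item, at most one log field and some SAP wording; the T2 form becomes slightly longer for intervention patients. A changed form may need the amendment route in Protocol 14.6 and translation where translated documents are used. The limits of the change should be stated: T2 goes only to patients who attended pre-assessment, counts only those who return it, and is requested within 7 days of receipt, so it does not cover a full month.
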